8.1.2 Minimal Residual Disease

If the subject's physical examination findings, laboratory evaluations, and radiographic evaluations suggest that PR, CR, or CRi has been achieved, a peripheral blood and bone marrow sample to evaluate MRD by flow cytometry should be done between 8-12 weeks from the time of supportive clinical assessments including CT imaging of suspected PR, CR, or CRi.

A peripheral blood and bone marrow sample testing for minimal residual disease (MRD) will be done at timepoints specified in the SOA. If MRD samples are not taken at the EoT visit, then it can be drawn at SFU visit.

Samples for the MRD tests will be sent to the central laboratory for analysis as per instructions in the laboratory manual. After FA and per Amendment 5.0, MRD tests are not mandatory and will be locally performed per clinical practice.

8.1.3 Clinical laboratory assessments

See [Table 11](#) for the list of clinical laboratory tests to be performed and to the SoA for the timing and frequency. All protocol-required laboratory assessments, as defined in the table, must be conducted in accordance with the laboratory manual and the SoA.

The investigator should make an assessment of the available results with regard to clinically relevant abnormalities. The laboratory results should be signed and dated and retained at centre as source data for laboratory variables.

Additional laboratory samples may be collected if clinically indicated at the discretion of the investigator. The date, time of collection and results (values, units and reference ranges) will be recorded on the appropriate eCRF.

The clinical chemistry, pregnancy test, hepatitis serology and serum immunoglobulin levels analyses will be performed locally at the visits as indicated in the SoA (see [Table 1](#), [Table 2](#), and [Table 3](#)), therefore sample volumes may vary according to local hospital practice. If screening assessment clinical chemistry and hematology are performed within 5 days prior to the baseline visit (i.e., first dose day), they do not need to be repeated at the baseline visit. All samples will be used up or disposed of after analyses.

Pregnancy tests are required only for women with childbearing potential. A urine or serum pregnancy test is acceptable. Pregnancy tests will be performed at Screening, on Cycle 1 Day 1, and at the safety-follow-up visit, and may be performed more frequently if required by local regulatory authorities

Hematology testing will be evaluated at the central laboratory and will include a complete blood count (CBC) with WBC differential including, but not limited to white blood cell count, hemoglobin, hematocrit, platelet count, ANC, and ALC. Any missing central laboratory blood samples should be redrawn as soon as possible. In the event that the missing central laboratory sample is unrecoverable, local laboratory results will be collected, if available, and entered in the clinical database for response or progression confirmation. After FA and per Amendment 5.0, hematology testing will be performed locally.

β 2-microglobulin: peripheral blood samples will be collected and sent to the central laboratory for β 2-microglobulin test. After FA and per Amendment 5.0, the testing is not required and will be locally performed per the discretion of investigator.

T/B/NK cell count (i.e., CD3, CD4, CD8, CD19, CD16/56) will be performed at the central laboratory. After FA and per Amendment 5.0, the testing is not required and will be locally performed per the discretion of investigator.

Cytogenetics and FISH Panel: screening peripheral blood will be sent to a central laboratory to be tested for 17p del, 13q del, trisomy 12, 11q del by FISH and stimulated karyotyping, the status of 17p del is mandatory to be tested by central lab during screening period. A blood sample for FISH evaluation will also be drawn at Cycle 7, and when a subject has disease progression (with PD confirmation from BICR, cytogenetic and genetic molecular prognostic molecules and FISH evaluation need to be performed after signing crossover ICF), at the EoT or SFU visits. If these samples are damaged during collection or shipment, they should be redrawn at the next subsequent visit. After FA and per Amendment 5.0, the testing is not required and will be locally performed per the discretion of investigator.

Genetic molecular prognostic molecules: screening peripheral sample will be sent to central laboratory for sequencing of immunoglobulin heavy-chain variable (IGHV) and p53 mutational status. A blood sample will also be drawn when a subject has disease progression (with PD confirmation from BICR, cytogenetic and genetic molecular prognostic molecules and FISH evaluation need to be performed after signing crossover ICF), at the EoT or SFU visits. After FA and per Amendment 5.0, the testing is not required and will be locally performed per the discretion of investigator.

Table 11 Laboratory Variables

Clinical Chemistry ^a	
Calcium	Urea or blood urea nitrogen
Chloride	Uric acid
Magnesium	Creatinine
Phosphate/Phosphorus	Total bilirubin
Potassium	Glucose
Sodium	Albumin
AST	Total protein
ALT	Triglycerides
Alkaline phosphatase (ALP)	Cholesterol
Gamma glutamyl transferase (GGT)	Lactate dehydrogenase (LDH)
Hematology ^b	
White blood cell (WBC) count with differential	Platelet count
Red blood cell (RBC) count	Absolute neutrophil count (ANC)
Hematocrit	Absolute lymphocyte count (ALC)
Hemoglobin	
Pregnancy Test (females of childbearing potential only)	
Urine human chorionic gonadotropin (hCG) or Serum βhCG	
Hepatitis B and C Testing ^c	
HBsAg	Hepatitis B surface antibody (HBsAb)
Anti-HBc	Hepatitis C (hepatitis C virus [HCV]) antibody
Hepatitis B PCR (clinically indicated)	Hepatitis C PCR (clinically indicated)
Other Tests	
T/B/NK Cell Count ^b	Serum immunoglobulin levels
β2-microglobulin ^b	
Cytogenetics and FISH Panel ^{b, d}	Genetic molecular prognostic molecules ^{b, e}

^a In case a subject shows an AST or ALT $\geq 3 \times \text{ULN}$ together with total bilirubin $\geq 2 \times \text{ULN}$ please refer to [Appendix D](#) 'Actions required in cases of increases in liver biochemistry and evaluation of Hy's Law,' for further instructions.

- b These tests will be performed at the central laboratory.
- c Hepatitis serology testing must include HBsAg, HBsAb, anti-HBc and hepatitis C (HCV) antibody. In addition, any subjects testing positive for anti-HBc must have quantitative PCR testing for HBV DNA during screening and every 3 months thereafter. Monitoring every 3 months should continue until 12 months after last dose of study drug(s) for Arm A and Arm C subjects. For Arm B subjects, monthly monitoring should continue until 12 months after last dose of Arm B treatments. (See [Table 1](#), [Table 2](#), and [Table 3](#), and exclusion criteria #8). Any subject with a rising viral load (above lower limit of detection) should discontinue study drug and have antiviral therapy instituted and a consultation with a physician with expertise in managing hepatitis B. Since IVIG may cause false positive hepatitis serology, monthly PCR testing is not required in subjects who are currently receiving or received prophylactic IVIG within 3 months before study enrollment and have a documented negative anti-HBc test before the initiation of IVIG therapy. PCR testing should be performed when clinically indicated (e.g., in the setting of rising transaminase levels). Refer to [Table 1](#), [Table 2](#) and [Table 3](#) regarding monitoring of subjects who are anti-HBc positive or who have a known history of HBV. Subjects with a known history of hepatitis C or who are hepatitis C-antibody positive should have quantitative PCR testing for HCV RNA performed during screening. No further testing is necessary if the PCR results are negative at screening.
- d Cytogenetics and FISH Panel include 17p del, 13q del, trisomy 12, 11q del by FISH and stimulated karyotyping.
- e Genetic molecular prognostic molecules panel include, but is not limited to, sequencing of p53 mutations, immunoglobulin heavy-chain variable (IGHV) mutational status.

8.1.4 B-Symptoms

B-symptoms are constitutional symptoms defined as any one or more of the following disease related symptoms or signs:

- Unintentional weight loss of 10% or more within the previous 6 months
- Significant fatigue (i.e., ECOG performance status 2 or worse; inability to work or perform usual activities)
- Fevers >100.5°F or 38.0°C for ≥2 weeks without other evidence of infection
- Night sweats for >1 month without evidence of infection

B-symptoms is part of tumor response assessment for CLL subjects per [Hallek 2018](#).

B-symptoms should not be reported as AEs. Worsening is generally considered a symptom (but not an objective criterion) of progression.

8.1.5

CCI [REDACTED]

[REDACTED]

8.1.5.1

CCI [REDACTED]

[REDACTED]

CCI

CCI

8.2 Safety assessments

Planned time points for all safety assessments are provided in the SoA.

8.2.1 Clinical safety laboratory assessments

Clinical safety laboratory assessments are included in [Table 11](#) and specified in the SoA for the timing and frequency.

For information on how AEs based on laboratory tests should be recorded and reported, see [Section 8.3.5](#).

Additional safety samples may be collected if clinically indicated at the discretion of the investigator. The date, time of collection and results (values, units and reference ranges) will be recorded on the appropriate CRF.

8.2.2 Physical examination

A physical examination will be performed and include an assessment of the following: height (screening only) and weight, and examination of the skin, eyes, ears, nose, throat, lungs, heart, abdomen, extremities, musculoskeletal, nervous, lymphatic system, and general appearance. The nervous system examination will include attention to neurologic signs and symptoms of PML. The lymphatic system examination will include examination of palpable lymph nodes and spleen and liver below the costal margin on the respective side. Only physicians should perform the lymphatic system examination. As much as possible, the same person should perform all the lymphatic exams for a given subject. Changes from baseline abnormalities should be recorded in medical note. New or worsened clinically significant abnormalities should be recorded as AEs on the Adverse Event eCRF.

Physical examination will be performed at timelines as specified in the SoA, investigators should pay special attention to clinical signs related to previous serious illnesses, new or worsening abnormalities may qualify as adverse events, see Section 8.3.5 for details.

8.2.3 Vital signs

Body temperature, pulse rate, respiratory rate and blood pressure will be assessed after the subject has rested in the sitting position.

Blood pressure and pulse measurements will be assessed with a completely automated device. Manual techniques will be used only if an automated device is not available.

Changes from baseline abnormalities should be recorded in subject notes. New or worsened clinically significant abnormalities should be recorded as AEs on the Adverse Event eCRF.

8.2.4 Electrocardiograms

Single 12-lead ECG will be obtained as outlined in the SoA (see Section 1.1) using an ECG machine that automatically calculates the heart rate and measures PR, QRS, QT, and QTc intervals. Study -related ECG should be done in supine position after the subject has been resting for at least 10 minutes. Additional ECG testing could be scheduled as clinically indicated, a standardized ECG machine should be used, and the subject should be examined using the same machine throughout the study if possible.

After paper ECGs have been recorded, the investigator or designated physician will review each of the ECGs and may refer to a local cardiologist if appropriate. A paper copy should be filed in the patient's medical records.

If an abnormal ECG finding at screening or baseline is considered to be clinically significant by the investigator, it should be reported as a concurrent condition. For all ECGs details of rhythm, ECG intervals and an overall evaluation will be recorded.

8.2.5 ECOG performance status

ECOG performance status will be assessed at screening, prior to the first dose of study treatment and per SoA thereafter according to ECOG criteria as shown in [Table 12](#).

Table 12 ECOG Performance Status Scale

Grade	ECOG
0	Fully active, able to carry on all pre-disease performance without restriction
1	Restricted in physically strenuous activity but ambulatory and able to carry out work of a light or sedentary nature, e.g., light house work, office work
2	Ambulatory and capable of all self-care but unable to carry out any work activities. Up and about more than 50% of waking hours
3	Capable of only limited self-care, confined to bed or chair more than 50% of waking hours
4	Completely disabled. Cannot carry on any self-care. Totally confined to bed or chair
5	Dead

8.3 Collection of adverse events

The principal investigator is responsible for ensuring that all staff involved in the study are familiar with the content of this section

The definitions of an AE or SAE can be found in [Appendix B](#).

AE will be reported by the subject (or, when appropriate, by a caregiver, surrogate, or the subject's legally authorized representative).

The investigator and any designees are responsible for detecting, documenting, recording, and reporting events that meet the definition of an AE.

8.3.1 Time period and frequency for collecting AE and SAE information

AEs and SAEs will be collected by the site from the time of signature of informed consent form throughout the treatment period and including the follow-up period. After the signing of the ICF and prior to the first dose of study treatment all SAEs, regardless of causality, must be reported to the sponsor. Collection and reporting of AEs and SAEs after the final DCO is described in [Section 8.3.11](#).

All AEs and SAEs will be reported from first dose of study treatment until 30 days after the last dose of study treatment or the start of new anticancer therapy (whichever comes first).

After this period, investigators should report SAEs that are believed to be related to the study treatment or any AEs of concern (deemed by the sponsor or investigator), regardless of causality to the study treatment as relevant.

All SAEs that occur during the reporting period should be followed to resolution or until the investigator assesses the subject as stable, or until the subject is lost to follow up or withdraws consent. Resolution/stable means the subject has returned to baseline state of health or the investigator does not expect any further improvement or worsening of the event.

Table 13 Guidance for Reporting Adverse Events

	AEs	SAEs	AESIs	AEs of concern
Signing of ICF – First dose of study treatment	Not reported (recorded as medical history)	Related (to study procedure) Unrelated	Not reported (recorded as medical history)	Not reported (recorded as medical history)
First dose of study treatment – 30 days after last dose of study treatment	Related	Related	Related	Related
	Unrelated	Unrelated	Unrelated	Unrelated
Post-30 days after last dose of study treatment	Not reported	Related	Not reported	Related
				Unrelated

All SAEs/AESIs will be recorded and reported to the sponsor or designee within 24 hours. The investigator will submit any updated SAE/AESI data to the sponsor within 24 hours of it being available.

Investigators are not obligated to actively seek AE or SAE data in former study subjects. However, if at any time after a subject’s last visit the investigator learns of any SAE, including a death, that is considered to be reasonably related to the study treatment or study participation, the investigator may notify the sponsor.

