7.1.1 Procedures for discontinuation of study treatment

The investigator should instruct the subject to contact the site before or at the time if study treatment is stopped. A subject that decides to discontinue study treatment will always be asked about the reason(s) and the presence of any AEs. The date of last intake of study treatment should be documented in the eCRF. All study treatment should be returned by the subject at their next on-site study visit or unscheduled visit. Subjects permanently discontinuing study treatment should be given locally available standard of care therapy, at the discretion of the investigator.

Discontinuation of study treatment, for any reason, does not impact on the subject's participation in the study. The subject should continue attending subsequent study visits and data collection should continue according to the study protocol. Patients who have

permanently discontinued from further receipt of IP will need to be discontinued from the IRT/RTSM.

An EoT visit is required for safety assessments for any subjects who permanently discontinue study treatment for any reason (except for death, lost to follow-up, or withdrawal of consent), including disease progression. The end of treatment visit is not required for subjects who discontinue from study treatment within 10 days of a scheduled study visit or if the EoT visit would be performed within 14 days of the safety follow-up visit. If the SFU visit is within ± 7 days of a regularly scheduled visit during the post-treatment phase, the visits may be combined into a single visit.

In addition to the EoT visit, an SFU visit should be conducted at 30 (+7) days after his or her last dose of all study drugs to monitor for resolution or progression of AEs and to document the occurrence of any new events, regardless of whether the subject receives a new anticancer therapy or demonstrates disease progression within this time frame. Refer to Tables 1-3, for the assessments required for the EoT and SFU visits.

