9.5.2 Safety analyses

Safety analyses will be performed using the safety analysis set. Unless noted otherwise, summaries will be based on safety data collected in the initial treatment period (i.e., for patients who cross over to Arm A, the safety data on or after receiving first dose of cross-over therapy will be excluded). Safety data on or after receiving first dose of cross-over therapy might be summarized separately, provided that there are a sufficient number of patients to warrant this.

All safety data will be listed.

Adverse Events

Adverse events will be coded using the most recent version of the Medical Dictionary for Regulatory Activities (MedDRA) that will have been released for execution at the sponsor/designee.

Safety data will be presented using descriptive statistics unless otherwise specified.

AEs will be presented for each treatment group by SOC and/or PT covering number and percentage of subjects reporting at least one event and number of events where appropriate.

AEs occurring prior to start of IP, treatment emergent AEs, and post-treatment AEs will be presented separately.

An overview of AEs will be presented for each treatment group the number and percentage of subjects with any AE, AEs with outcome of death, serious AEs, and AEs leading to discontinuation of IP, as well as AEs leading to IP dose delays, AEs leading to IP dose reduction as well as the number of individual occurrences in those categories.

Separate AE tables will be provided taken into consideration relationship as assessed by the investigator, CTCAE grading, seriousness, death and events leading to discontinuation of IP as well as other action taken related to IP, events of special interest, Other significant adverse events.

An additional table will present number and percentage of subjects with most common AEs (frequency of >5%).

Key subject information will be presented for subjects with AEs with outcome of death, serious AEs, and AEs leading to discontinuation of IP.

An AE listing for the safety analysis set will cover details for each individual AE.

Full details of AE analyses will be provided in the SAP.

Treatment Emergent

The following events are considered treatment emergent:

- Adverse events with an onset date on or after first dose of IP, and within 30 days after last dose of IP
- Worsening of pre-existing events on or after first dose of IP, and within 30 days after last dose of IP

Clinical Laboratory Tests

Data Summary Methods

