### 3.5.2 Adverse events

AEs will be collected throughout the study, from date of informed consent until 30 days after the last dose of study drug. SAEs will be collected from the date of informed consent. The following events will be considered treatment emergent:

- Adverse events with an onset date on or after first dose of study drug, and within 30 days after last dose of study drug or the initiation of a subsequent therapy (including crossover treatment), whichever occurs first.
- Worsening of pre-existing events on or after first dose of study drug, and within 30 days after last dose of study drug or the initiation of a subsequent therapy (including crossover treatment), whichever occurs first.

The Medical Dictionary for Regulatory Activities (MedDRA) (using the latest or current MedDRA version) will be used to code the AEs. AEs will be graded according to the

National Cancer Institute Common Terminology Criteria for AEs (using the NCI CTCAE version 5.0).

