### **Analyses for crossover period**

Summary tables from the above AE section, including AEs, AEs leading to death, AEs leading to dose discontinuation, serious AEs, and overall summary of ECIs, will be repeated for patients in the crossover period, provided the crossover period includes at least 10 patients. Otherwise, crossover related safety data will be listed only.

The AE summary tables for crossover patients will include all AEs that occurred after the start of crossover treatment up until the end of the 30 day follow-up period. The 30 day follow-up period will be defined as 30 days following discontinuation of treatment.

In addition to AE summaries, selected summaries of clinical laboratory parameters, vital signs and ECG data might be repeated for crossover patients only provided at least 10 patients receive crossover therapy.

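### Protocol 8.3.1 ends full AE/SAE reporting at new anticancer therapy but Table 13 in the same section does not; separately, the SAP cuts the treatment-emergent window where the protocol does not, and does not declare it

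*Protocol*

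**What the plan says.** **Reporting.** Protocol 8.3.1 states that all AEs and SAEs are reported from first dose "until 30 days after the last dose of study treatment or the start of new anticancer therapy (whichever comes first". After that, "investigators should report SAEs that are believed to be related to the study treatment or any AEs of concern". Table 13, a few lines below, labels its main period "First dose of study treatment – 30 days after last dose of study treatment"; in that row AEs, SAEs and AESIs are reported whether related or not, and new therapy is not mentioned.

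**Visit.** Protocol 7.1.1 sets a safety follow-up visit at 30 (+7) days after last dose, in part "to document the occurrence of any new events, regardless of whether the subject receives a new anticancer therapy".

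**Treatment-emergent definition.** Protocol 9.5.2 counts "Adverse events with an onset date on or after first dose of IP, and within 30 days after last dose of IP". SAP 3.5.2 counts events "within 30 days after last dose of study drug or the initiation of a subsequent therapy (including crossover treatment), whichever occurs first". The SAP applies the same cut to laboratory data (4.2.6.3), vital signs (4.2.6.4) and ECOG status (4.2.6.5), whereas protocol 9.4.2 defines on-treatment as running to 30 days after discontinuation.

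**Collection and listing in the SAP.** The collection sentence in SAP 3.5.2 runs to 30 days after last dose without a cut, and gives SAEs a start but no end. SAP 4.2.6.2 lists all AEs and flags those that begin after crossover or any other subsequent therapy.

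**Declared changes.** SAP section 6 names the China analysis sets and the nodular partial response clarification only.

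**The concern.** A site cannot follow both the 8.3.1 sentence and Table 13 for a patient who starts another anticancer drug inside the 30 days. Sites that read different passages will report differently, and an event that was never recorded cannot be recovered by an analysis rule.

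The second difference lies in the tables. Even with identical records, the protocol's definition and the SAP's definition give different treatment-emergent counts, and a reader who relies on SAP section 6 would not know that the definition had moved.

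Both matter most where treatment stops because of progression or toxicity, since that is when the next therapy is likely to follow soon. Acalabrutinib continues until progression or another stopping criterion; rituximab plus chlorambucil ends after at most 6 cycles (protocol 4.1). A shorter window could therefore trim one arm's safety record more than the other's in an open-label comparison.

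**Working it through.** The plan states no figure on this point, so the check is a comparison of passages, followed by an illustration of direction.

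**Step 1. Sort the passages by what they govern.**

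| Purpose | Cut at new therapy | Full 30 days |
|---|---|---|
| Reporting or collection | Protocol 8.3.1 sentence | Protocol Table 13; SAP 3.5.2 collection sentence (AEs) |
| Safety visit | none | Protocol 7.1.1 and the footnotes to the schedules of assessments |
| Treatment-emergent AEs | SAP 3.5.2 | Protocol 9.5.2 |
| On-treatment laboratory, vital signs, ECOG | SAP 4.2.6.3 to 4.2.6.5 | Protocol 9.4.2 |
| Crossover-period AEs | none | Protocol 6.8; SAP 4.2.6.2 |

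Within a row, the direct conflicts are 8.3.1 against Table 13, and protocol 9.5.2 (with 9.4.2) against the SAP. The visit row is not itself a reporting rule, but a visit meant to document new events "regardless of whether the subject receives a new anticancer therapy or demonstrates disease progression within this time frame" only makes sense if those events are recorded. The crossover row is consistent across the documents: the SAP's "all AEs that occurred after the start of crossover treatment up until the end of the 30 day follow-up period" follows the protocol's 30-day crossover follow-up.

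**Step 2. Follow one hypothetical patient.** Acalabrutinib stops on day 0, the next drug starts on day 10, and an event not related to study drug begins on day 20.

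- Non-serious AE: outside full reporting under the 8.3.1 sentence (20 > 10) unless deemed of concern; reported under Table 13 (20 ≤ 30).
- Unrelated SAE: the same split. Protocol 8.4.1 requires all SAEs regardless of causality, so it sides with Table 13.
- Non-serious ventricular arrhythmia (AESI): the same split. Protocol 8.3.10 requires it regardless of seriousness or causality, so it too sides with Table 13.
- Related SAE, or AE of concern: reported under both.
- Death: documented under 8.3.9 in either case.
- Treatment-emergent status, if recorded: yes under protocol 9.5.2; no under SAP 3.5.2.

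**Step 3. Illustrate the direction by arm.** Inputs: median PFS of 30 and 90 months, 75 patients per arm and 30 months' accrual (protocol 9.2), with analysis at about 45 months (protocol 4.4). Assumptions: exponential PFS, uniform accrual, PFS events standing in for stopping treatment, and every such patient starting new therapy within 30 days of last dose.

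- Arm A: λ = ln 2 / 90 = 0.0077 per month, with follow-up spread over 15 to 45 months. Expected events = 75 × [1 − (e^(−15λ) − e^(−45λ)) / (30λ)] = 15.3, or 14.5 with the SAP's 5% dropout by 14 months.
- Arm B: λ = ln 2 / 30 = 0.0231 per month. The last scheduled chlorambucil dose is on day 5 × 28 + 15 = 155. Expected events by day 155 (5.09 months) = 75 × (1 − e^(−5.09λ)) = 8.3; by day 155 + 30 = 185 (6.08 months), 9.8.
- Arm A share: from 14.5 / (14.5 + 9.8) = 60% to 15.3 / (15.3 + 8.3) = 65%.

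For the treatment-emergent comparison the Arm A share would be higher, because protocol 9.5.2 already excludes data from the first crossover dose. The illustration gives a direction only; it does not estimate how many events are affected.

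**The case against.** The strongest reply is that the practical gap is narrow. After the 8.3.1 window closes, related SAEs and AEs of concern are still reported; 8.4.1 asks for all SAEs and 8.3.10 for all AESIs. What rests solely on the disputed sentence is therefore mainly other non-serious AEs. The SAP's plan to flag events after other subsequent therapies suggests that such records were expected in the database. Ending the treatment-emergent period at the next anticancer drug is also a respectable choice, and protocol 9.5.2 leaves full details of AE analyses to the SAP.

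Most of this stands. It narrows what is at risk and leaves the choice of primary treatment-emergent window open. It does not remove the contradiction inside 8.3.1, nor the undeclared difference between protocol and SAP. A site that follows the 8.3.1 sentence would still leave out events that Table 13 requires.

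A reader might infer more, and the documents do not support it:

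- **That Arm A deaths drop out.** Protocol 8.3.9 covers deaths during and after follow-up, and SAP 3.1 summarises death over the randomised period, the crossover period and the whole study. At most, a death's classification as the outcome of a treatment-emergent AE changes.
- **That the SAP stops collecting AEs at new therapy.** Only its treatment-emergent definition is cut.
- **That the loss falls almost wholly on Arm A.** Arm B patients can also stop early for progression or toxicity; even the illustration above gives 60-65%.
- **That a patient count can be given.** Assuming 10 to 25 Arm A discontinuations, half of them starting new therapy at about day 10, gives 5 to 12 patients each losing 30 − 10 = 20 days, but none of those inputs is in the documents.

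**Conclusion.** The point holds in two parts. First, protocol 8.3.1 contradicts its own Table 13 on when full AE/SAE reporting ends, and the surrounding passages (7.1.1, 8.3.10, 8.4.1, the SAP 3.5.2 collection sentence and the SAP 4.2.6.2 flag) fit the uncut version. Second, the treatment-emergent and on-treatment windows are uncut in the protocol and cut in the SAP, without declaration in SAP section 6.

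The exposure is at most 30 days per affected patient. A heavier effect on Arm A is probable, given treatment until progression against at most 6 cycles, but this is an inference from the design. The number of affected patients or events cannot be computed, because the documents give no rate of new therapy within 30 days of last dose. The primary PFS analysis is not touched. This should be corrected and disclosed; it is a question of consistent safety reporting, not of the trial's validity.

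**What to change.** 1. Reconcile the 8.3.1 sentence with Table 13 so that one reporting window, to 30 days after last dose, applies to all AEs and SAEs, with the start date of any new therapy recorded. That date is already needed for PFS censoring and time to next therapy.
2. State one treatment-emergent window for protocol and SAP, and bring the laboratory, vital-sign and ECOG windows into line with it. Show the other window as a supportive AE table, using the flag already planned in SAP 4.2.6.2.
3. List any remaining difference from the protocol in SAP section 6.
4. Amended wording cannot change what was collected for the final analysis, whose data cut-off was 03Jan2024. Establish which reporting rule sites followed and say so in the clinical study report. The wording still matters for follow-up under Amendment 5.0.

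The cost is text changes, a supportive table and a query to sites. The safety visit is already scheduled. The downside is a few more AE records, some of them due to the next therapy; the flag separates these.
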